10.3 Termination of the Study

The study may be terminated prematurely due to safety reasons by the DMC (Section 7).

Additional reasons for study termination include, but are not limited to, the following:

- The local or national regulatory agency requests a termination of the study.
- It has been determined that the risk level associated with the experimental drug is significant and warrants termination of the study.
- Windtree, for reasons other than safety, may terminate the study at any time by written notice of intended termination provided at least 30 days before termination.
- The PI or IRB/IEC, for reasons other than safety, may terminate participation of this clinical site in the study by written notice of intended termination provided at least 30 days before termination.

- Any other clause described in the individual site Clinical Study Agreement (eg, if ICH GCP guidelines or other regulatory procedures are not followed or if enrollment rate is not sufficient to meet study goals).

10.4 Replacement of Subjects

Subjects who discontinue treatment early or who are withdrawn from the study will not be replaced, unless required by the DMC.

11 PROTOCOL VIOLATIONS/DEVIATIONS

A protocol deviation occurs when the PI or any other site staff assigned to the study fail to adhere to any protocol requirement. Protocol deviations include collection of information outside a collection window or failure to collect non-critical information.

A protocol violation occurs when the PI fail to adhere to any significant protocol requirement affecting the inclusion, exclusion, subject safety, and primary endpoint criteria. Protocol violations include but are not limited to the following:

- Failure to meet eligibility criteria
- Use of a prohibited concomitant medication (Section [8.6](#))
- Failure to comply with ICH GCP guidelines

Windtree will determine if a protocol violation will result in withdrawal of a subject, prior to unblinding of the study treatments.

When a protocol violation or deviation occurs, the site monitor will discuss it with the PI. All protocol violations and deviations will be documented and tracked.

12 ETHICS

This study will be conducted according to the United States and ICH regulations and guidelines (21 Code of Federal Regulations [CFR] Part 50, *Protection of Human Subjects*, 21 CFR Part 56, *Institutional Review Boards*, 21 CFR Part 312, *Investigational New Drug Application*, and ICH E6, *Guideline for Good Clinical Practice*) as well as all applicable local, state, and federal regulations and guidelines regarding the conduct of clinical studies. In addition, this study will be conducted in accordance with the ethical principles included in the World Medical Assembly (WMA) Declaration of Helsinki, *Ethical Principles for Medical Research Involving Human Subjects* adopted by the 18th WMA General Assembly, Helsinki, Finland, June 1964, and amended most recently by the 64th WMA General Assembly, Fortaleza, Brazil, October 2013.

Throughout this section the term “Clinical Investigator” will be defined, in accordance with 21 CFR 54, as any listed or identified PI or subinvestigator who is directly involved in study dosing or evaluation of research subjects. PIs or subinvestigators must be listed on Form FDA 1572, if applicable, and documented as appropriate on the delegation of authority signature log.

12.1 Institutional Review Board/Independent Ethics Committee/Research Ethics Board

The protocol, including any amendments and the ICF, will be submitted to the appropriate IRB/IEC for each study site for approval to conduct the study. Before the initiation of the study at each study site, Windtree must be provided with a copy of the IRB/IEC approval to conduct the study. This approval must refer to the study by exact protocol title and number and should identify the documents reviewed and the date of review.

Protocol and ICF modifications or changes may not be initiated without prior written IRB/IEC approval, except when necessary to eliminate immediate hazards to the study subjects or when the change(s) involves only logistical or administrative aspects of the study. Such modifications will be submitted to the IRB/IEC and written verification that the modification was submitted and subsequently approved should be obtained. A site must receive approval from Windtree on any ICF modification before submission to the IRB/IEC for approval and subsequent implementation at the study site. Protocol modifications (ie, amendments) may only be enacted by Windtree.

The IRB/IEC must be informed of revisions to other study-related documents or study information that was originally submitted for review. Revised study documentation and related informational updates may include but are not limited to the following:

1. Serious and/or unexpected AEs occurring during the study (reported in accordance with the SOPs and policies of the IRB/IEC)
2. Any new study information that may adversely affect subject safety or study conduct
3. Annual study updates or IRB/IEC requests for reassessment of the study
4. Timely communication of significant actions and related findings from the DMC (to include study enrollment holds or expansion, protocol amendments, or early study closure).
5. Notification of major study/site milestones to include study/site closure

12.2 Informed Consent Form of Study Subject

A signed written ICF will be obtained in accordance with the Declaration of Helsinki, ICH GCP, 21 CFR 50 Subpart B, 2 and 21 CFR 56, Subpart A), HIPAA (where applicable), and local regulations.

The PI will prepare the ICF (to include HIPAA authorization [where applicable]) based on an ICF template provided by Windtree. Completed site-based ICFs must be acceptable to Windtree and be approved by the IRB/IEC. The PI will send an IRB/IEC approved copy of the ICF to Windtree for the study file.

The subject's legally authorized guardian will be provided a consent form describing this study and be provided sufficient information to make an informed decision about the subject's participation in this study. The formal permission of a subject's legally authorized guardian, documented on the IRB/IEC-approved consent form (and any other locally required documents), must be obtained before the performance of any study-related activity, including the cessation of any medications or procedures. The consent form must be signed and dated including the time of consent by the subject's legally authorized guardian, the investigator-designated research professional obtaining the consent, and, if applicable, an impartial witness.

Time to treatment is potentially an important factor in the success of non-invasive delivery of surfactant. Because of this and other operational factors, antenatal consent should be obtained where permitted. Assent of the subject will not be sought, since all subjects are neonates and not capable of providing assent.

12.3 Financial Disclosure

The FDA has issued regulations (21 CFR Part 54, *Financial Disclosure by Clinical Investigators*) that require sponsors to submit complete and accurate certification or disclosure statements to certify the absence of certain financial interests of clinical investigators and/or to disclose those financial interests, as required, when clinical studies are submitted to FDA in support of marketing approval. These regulations are intended to ensure that financial interests and arrangements of clinical investigators, that could affect reliability of data submitted to FDA in support of marketing approval, are identified and disclosed by the sponsor.

Clinical investigators will be asked to disclose proprietary (eg, patent, licensing agreement) and financial (eg, stock options, royalty) interests as they pertain to Windtree, before participating in the study. In addition, clinical investigators will be required to consult with Windtree before acquiring any financial interest in the company and must disclose any change in their proprietary or financial interests, if it occurs during the course of the study and for 1 year following study completion. The requirement for proprietary and financial disclosure also includes any ownership by the spouse or any dependent subject of the clinical investigator.

If FDA determines that the financial interests of any clinical investigator raise serious questions about the integrity of the data, FDA will take any action it deems necessary to ensure the reliability of the data, including:

- Initiating agency audits of the data derived from the clinical investigator in question
- Requesting that the sponsor submit further data analyses (eg, to evaluate the effect of the clinical investigator's data on overall study outcome)
- Requesting that the applicant conduct additional independent studies to confirm the results of the questioned study
- Refusing to treat the covered clinical study as providing data that can be the basis for an agency action

If the sponsor does not include certification or disclosure, or both (as required), or does not certify that it was not possible to obtain the information, the FDA may refuse to file the New Drug Application (NDA).

13 STATISTICAL METHODS AND DETERMINATION OF SAMPLE SIZE

It is anticipated that up to 130 subjects (approximately 50% in each treatment group) will be enrolled into the study.

A complete outline of the all planned analyses for the study, including the handling of missing data, is provided in the Statistical Analysis Plan for this protocol.

13.1 Estimand

The primary estimand for this study is the occurrence of intubation for the purpose of mechanical ventilation or surfactant administration in preterm neonates 28 to 32 weeks PMA in the modified intent-to-treat (mITT) population (all randomized subjects that received study medication). Intercurrent events include 1) treatment administration interruptions and 2) intubations for reasons other than MV or surfactant administration. Intercurrent events will be evaluated using the hypothetical (primary analysis), treatment policy, and principal stratum strategies.

In regard to the hypothetical strategy (primary analysis), if a subject is intubated for a reason other than MV and/or surfactant administration (eg, surgical procedure, elective surgery), it is not possible to know if the subject would have ultimately required MV and/or surfactant administration. However, in order to maximize non-missing data, if the subject is extubated within 24 hours and did not receive surfactant while intubated, they will continue to be followed to determine if they have respiratory failure due to RDS (ie, intubated for MV and/or surfactant administration). Otherwise, they will not be counted in the denominator and their response to therapy will be considered missing for the primary analysis.

For the treatment policy strategy, the occurrence of either intercurrent event is irrelevant and the primary variable will be used regardless of whether an intercurrent event occurs.

Finally, for the principal stratum strategy, if a subject's treatment was interrupted, there is an increased risk that the efficacy of the treatment will be impacted in a negative way. Thus, in the principal stratum strategy, these subjects will be excluded from the analysis. It should be noted that this strategy may lead to a biased estimation as interruptions, if they occur, can only occur with the active treatment. However, based upon testing of the current version of the ADS, it is expected that treatment interruptions will be exceedingly rare.

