9. A need for intubation and/or invasive mechanical ventilation at any time before enrollment into the study.
10. The administration (or plan for administration) of any the following:
 - a) Another investigational agent or investigational medical device
 - b) Any other surfactant agent
 - c) Systemic corticosteroids (other than antenatal steroids)
11. Presence of air leak (pneumothorax, pneumomediastinum, pneumopericardium, subcutaneous emphysema, or definite evidence of pulmonary interstitial emphysema [PIE]) on the baseline chest radiograph or diagnosed via ultrasound or illumination.

Concomitant Medications:

All concomitant medications administered to the subject from birth until 36 weeks PMA, hospital discharge, hospital transfer, or death (whichever occurs first) will be recorded in the electronic case report form (eCRF).

Medications required for the general care of the subject are permitted with the exception of investigational agents, investigational medical devices, or any SRT before randomization. Commercially available SRTs, following study treatment, may be administered as medically indicated (ie, “rescue surfactant”). Study subjects who receive any commercial SRT while on-study will be considered treatment failures but will continue to be followed until study completion. Postnatal steroids are not permitted unless clear medical need is determined. Use of caffeine citrate or other methylxanthines is recommended.

Safety and Tolerability Endpoints:

The safety and tolerability endpoints will be assessed during the primary phase through 36 weeks PMA, hospital discharge, hospital transfer, or death, whichever occurs first, as described below.

1. All-cause mortality through 28 days of life and 36 weeks PMA
2. AEs, including adverse device effects (ADEs). SAEs that are ongoing at 36 weeks PMA will be followed for an additional 30 days
3. Concomitant medications

4. Use of any type of respiratory support (invasive or non-invasive), including an oxygen requirement ($\text{FiO}_2 > 0.21$) or the need for endotracheal intubation and MV
5. Complications of prematurity, including air leak
6. Physical examinations
7. Assessments of the following:
 - a. Vital signs
 - b. FiO_2
 - c. SpO_2
 - d. CPAP/PEEP
 - e. Chest radiography prior to intubation

Early
Discontinuation of
Treatment:

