4.3 Efficacy Endpoints

4.3.1 Primary Endpoint

The primary endpoint for this study is the number of subjects with respiratory failure due to RDS or death within the first 28 days of life. Respiratory failure due to RDS is defined as intubation (including intratracheal catheter placement) for MV and/or surfactant administration.

Respiratory failure due to RDS or death will be categorized as follows:

- Early respiratory failure: Respiratory failure or death occurring \leq 72 hours after birth
- Late respiratory failure: Respiratory failure or death occurring $>$ 72 hours and \leq 28 days after birth

Subjects meeting the criteria of respiratory failure due to RDS must continue to be followed for all safety evaluations as outlined in Section 1.2 until the time the subject completes the study or withdraws (Section 10.2).

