8.6.1 Use of Additional Surfactant Replacement Therapies

Following randomization, commercially available SRT may be administered to subjects whose respiratory status has deteriorated such that conventional SRT is in the subject's best medical interest in the judgment of the investigator (ie, "rescue surfactant"). Because conventional SRT requires endotracheal intubation (even if a tube other than an endotracheal tube is used, such as a thin catheter), subjects receiving commercially available SRT will be considered intubated and to have respiratory failure due to RDS (see Section 4.3.1). Such subjects remain in the study and are followed until study completion but will not receive study treatment.

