1.2.1 Efficacy Objective

The primary estimand for this study is the occurrence of intubation for the purpose of mechanical ventilation or surfactant administration in preterm neonates 26 to 32 weeks PMA in the intent-to-treat (ITT) population (all randomized subjects). Intercurrent events include 1) treatment administration interruptions and 2) intubations for reasons other than MV or surfactant administration. Due to the small number of subjects as a result of the termination of the study, and that statistical testing will not be performed, intercurrent events will not be evaluated.

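### Protocol 13.1 drops from the primary analysis some infants with an observed endpoint event (rescue surfactant while intubated for another reason, or death by day 28) that sections 1.1, 4.3.1 and 8.6.1 count as failures

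*Protocol*

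**What the plan says.** **Endpoint.** Protocol 4.3.1 defines the primary endpoint as "the number of subjects with respiratory failure due to RDS or death within the first 28 days of life". It adds: "Respiratory failure due to RDS is defined as intubation (including intratracheal catheter placement) for MV and/or surfactant administration".

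**Rescue surfactant.** Section 1.1, under concomitant medications: "Study subjects who receive any commercial SRT while on-study will be considered treatment failures". Section 8.6.1: "subjects receiving commercially available SRT will be considered intubated and to have respiratory failure due to RDS". Section 8.6.1 refers the reader to 4.3.1, so its classification is meant for the primary endpoint.

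**Intubation for another reason.** Section 13.1 treats this as an intercurrent event and names three approaches: "Intercurrent events will be evaluated using the hypothetical (primary analysis), treatment policy, and principal stratum strategies". Under the primary one, "if the subject is extubated within 24 hours and did not receive surfactant while intubated, they will continue to be followed". If either condition fails, the consequence is: "Otherwise, they will not be counted in the denominator and their response to therapy will be considered missing for the primary analysis". The reason given is that one cannot tell whether such an infant would have gone on to need ventilation or surfactant.

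**SAP.** The SAP was written after enrolment stopped at 12 infants. Section 1.2.1 says "intercurrent events will not be evaluated". Section 4.1 bases efficacy on all enrolled infants, 4.2.1 counts all-cause death within 28 days, and 4.3 imputes nothing. The 24-hour rule is neither repeated nor withdrawn.

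**The concern.** Two rules in the same protocol give different primary outcomes for the same infant. One intubated for a surgical procedure and then given commercial surfactant is a failure under 1.1 and 8.6.1, but missing under 13.1. Nothing in the protocol says which rule prevails.

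Death raises a similar problem. Section 13.1 words its estimand in terms of intubation and makes no exception for death. Read as written, an infant excluded under the rule who dies by day 28 also leaves an endpoint that includes death.

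The treatment difference is at stake. Protocol 13.2 and SAP 2.2.3 intend it for planning further studies and as supporting evidence of efficacy. The removals depend on what happens after randomisation, so they need not balance between arms.

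**Working it through.** **1. The rules side by side**

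Each row is an infant intubated for a reason other than ventilation or surfactant.

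| Subsequent course | 13.1 primary analysis | 1.1 and 8.6.1 | 4.3.1 |
|---|---|---|---|
| Extubated within 24 h, no surfactant | Kept and followed | Silent | Event only if a later one occurs |
| Commercial surfactant while intubated | Missing | Failure | Event through the 8.6.1 cross-reference |
| Intubated over 24 h, no surfactant, dies by day 28 | Missing | Silent | Event (death) |
| Intubated over 24 h, no surfactant, survives | Missing | Silent | Not an observed event on that intubation alone |

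Rows two and three are the contradiction. Row four is not.

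**2. Is the surfactant in 13.1 the same thing as the commercial surfactant in 8.6.1?** Section 8.7.3 allows study treatment only through the study nCPAP device and interface. Surfactant given while an infant is intubated is therefore in practice a commercial product, and the two rules meet.

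**3. Does the rationale in 13.1 cover these infants?** It rests on an unknown outcome. In rows two and three an endpoint component has been observed. No hypothetical outcome is estimated; the record is removed.

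**4. Size**

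The plan gives no figure for the number affected, so this is illustration only. Inputs:

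- 65 per arm (protocol 13.4: up to 130, about half in each group).
- Rates of 44% control and 32% active, from protocol 3.2.3.5. These are the earlier phase 2b study's nCPAP failure rates in infants without treatment interruptions. In the full mITT population of that study all groups were at 44%.
- Rounded to whole infants: control 29/65 = 44.6%, active 21/65 = 32.3%, difference 12.3 points.
- k, the number of events removed from an arm: assumed.

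Formula: rate after removal = (events − k)/(n − k).

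| k | Active after removal | Control after removal | Difference: active only | Control only | k in each arm |
|---|---|---|---|---|---|
| 1 | 20/64 = 31.25% | 28/64 = 43.75% | 13.4 | 11.4 | 12.5 |
| 3 | 18/62 = 29.0% | 26/62 = 41.9% | 15.6 | 9.6 | 12.9 |
| 5 | 16/60 = 26.7% | 24/60 = 40.0% | 17.9 | 7.7 | 13.3 |

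Equal removals up to five per arm move the difference by about 1.0 point (13.3 − 12.3). One-sided removals of five move it by 5.6 points upward (17.9 − 12.3) or 4.6 downward (12.3 − 7.7).

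With very few infants one reclassification shows at once. If an arm had six infants and three events (both assumed, since the SAP does not give the split of the 12), dropping one event changes 3/6 = 50% to 2/5 = 40%.

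**The case against.** The strongest reply is that the rule appears not to operate in the analysis that will be reported. Protocol 13 sends the full analysis outline, missing data included, to the SAP. The SAP sets intercurrent events aside, analyses all enrolled infants, counts all-cause death and plans no testing. This largely stands. For the 12 enrolled infants, death is already handled. What stays open is narrower: SAP 4.2.1 counts infants who need intubation for surfactant administration, which does not settle surfactant given to an infant already intubated for something else.

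A second reply is that 13.1 also plans a treatment-policy analysis, which keeps these infants. That is correct and limits the damage, but it is not the analysis labelled primary.

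Third, 8.6.1 introduces rescue surfactant for infants whose respiratory status has deteriorated, so it might be read as not covering surfactant given around a procedure. Its classifying sentence is general, however, and 1.1 refers to any commercial product.

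A reader might go further and infer that 1.1 and 8.6.1 contradict the whole exclusion, including the limb for more than 24 hours. They do not, because both concern surfactant only. Without surfactant or death, an infant kept intubated after surgery has no observed failure under 4.3.1 on that intubation alone. How to handle that infant is an estimand choice for which 13.1 gives a reason.

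A reader might also infer that the rule always lowers the failure rate. It does so only when the infants removed have had an event. Removing one non-event raises it: 29/65 = 44.6% becomes 29/64 = 45.3%.

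**Conclusion.** The contradiction is real but limited to two groups: infants given commercial surfactant while intubated for another reason, and otherwise-excluded infants who die by day 28. For both, the primary analysis in 13.1 discards an event that other sections of the protocol count. The effect is to lower the event rate in the arm concerned and to move the treatment difference in either direction.

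The conclusion rests on the text alone. The sizes shown depend on assumed counts, and the documents do not say how many infants are affected; among the 12 enrolled it may be none. The documents do not support saying that the final descriptive analysis will delete infants, or that its reported rates are biased. Severity is minor to moderate: a clear defect in the protocol's primary rule, with one open classification question in the SAP.

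**What to change.** **Protocol 13.1.** Reconcile it with 1.1, 4.3.1 and 8.6.1. State that commercial surfactant or death by day 28 counts as a primary event whatever the first reason for intubation. Limit the exclusion to infants with neither event.

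**SAP 4.2.1.** State that commercial surfactant given to an already-intubated infant within 28 days is an event, and that the denominator exclusion in protocol 13.1 is not applied. All-cause death needs no change there.

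**Left as a separate choice.** Infants intubated for more than 24 hours with neither surfactant nor death are outside this correction. The treatment-policy analysis planned in 13.1 already retains them.

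**Cost.** A sentence or two in each document. No new data item is needed: surfactant use is recorded with concomitant medications (protocol 8.6) and deaths with date and time (4.4). The rule also avoids relying on the reason for intubation, which 8.7.5.1 requires through Study Day 7 but 8.7.5.2 does not list from Day 8. With 12 infants, the planned listings of concomitant medications and respiratory support would show whether any infant is affected. If one is, the failure rate in that arm will be higher than under the exclusion.
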